12.3.2 Intention to Treat Analysis Population

The Intention To Treat (ITT) analysis population is defined as all subjects enrolled in the study, by assigned treatment, regardless of the treatment actually received.

The ITT population of evaluable (i.e., not Roll-In) subjects will be used for the primary analysis of secondary performance endpoints and Other Measures. The ITT population will also be used for a secondary analysis of the primary and secondary efficacy endpoints and the primary and secondary safety endpoints.

12.3.3 As Treated Analysis Population

The As Treated (AT) analysis population is defined by the treatment actually received, rather than the treatment assigned. In the AT population, subjects in whom vascular access in the

contralateral femoral artery has been established for the intended deployment of the TriGuard HDH or TriGUARD 3 device will be analyzed as part of the Intervention group, and subjects in whom the TAVI procedure is initiated (but no vascular access for intended deployment of the TriGuard HDH or TriGUARD 3 is established) will be analyzed as part of the Control group.

The AT population will be used for the primary analysis of all primary and secondary safety endpoints. The AT population will also be used as the secondary analysis population for the secondary performance endpoints and Other Measures.

12.3.4 Per Treatment Population

The Per Treatment (PT) analysis population is defined as subjects in the Intervention group in whom device positioning is maintained until final procedure with complete cerebral coverage, and all Control group subjects.

The PT population will be used for an additional analysis of the primary and secondary efficacy endpoints and other measures.

12.3.5 Roll-In Patient Population

The Roll-In (RI) patient population is defined as all subjects who undergo TAVI with the TriGuard HDH or TriGUARD 3 prior to enrollment of the first evaluable subject at each investigational site. Each investigational site without prior experience with the TriGuard device (minimum of 2 prior cases) will enroll a minimum of 2 RI subjects. RI subjects will not be randomized to a treatment arm, but will undergo TAVI with the embolic protection device and will undergo all protocol-specified follow-ups.

For the purposes of analysis, a subject is considered enrolled in the Roll-In phase of the study when:

- The patient has been judged to meet all inclusion and no exclusion criteria, and has signed a Patient Informed Consent form
- The TriGuard HDH or TriGUARD 3 device has been introduced into the patient's bloodstream

The RI patient population will be used for a separate analysis of all primary and secondary endpoints and Other Measures. Additional analyses will evaluate primary and secondary endpoints in the pooled population of RI Subjects plus Evaluable Subjects.

12.4 Method of Analysis and Reporting

12.4.1 Baseline Characteristics

The following data will be summarized using descriptive statistics and presented by treatment group for eITT (Roll-In subjects are excluded), ITT (Roll-In subjects are excluded), AT (Roll-In subjects are excluded), PT (Roll-In subjects are excluded), and Roll-In analysis sets. Descriptive statistics for continuous variables will include mean, median, standard deviation, minimum, maximum, and sample size for each treatment group. Binary variables will be summarized using frequencies, percentages, and sample size for each treatment group.

- Baseline demographics
- Baseline comorbidities, risk factors and medical history
- Cardiac risk factors, angina status and cardiac history
- Procedural characteristics

- Device details

12.4.2 Primary Safety Endpoint

The primary safety hypothesis is that the rate of the Combined Safety Endpoint (defined according to VARC 2 as the composite of death, stroke, life-threatening or disabling bleeding, AKI [Stage 2/3], coronary artery obstruction requiring intervention, major vascular complication, and valve-related dysfunction requiring repeat procedure) at 30 days in the group undergoing TAVI with the TriGuard HDH or TriGUARD 3 system (Intervention group) is significantly less than the Performance Goal (PG). The following analysis will be carried out in the AT (primary analysis population) and ITT populations including Roll-ins.

The primary safety analysis will assess if the Intervention group's safety endpoint rate is significantly less than 34.4% using a one-sample z-test of proportions. Specifically, the null and alternative hypotheses to be tested are:

$$H_0: \pi \geq 0.344$$

$$H_1: \pi < 0.344$$

where π is the true, unknown, safety event rate for the Intervention arm.

The number and percentage of patients in each group experiencing the safety endpoint rate will be presented for each treatment; in addition, one-sided 95% confidence intervals of the percentage will be presented, based on the normal approximation to the binomial distribution. For the intervention group, the above null hypothesis will be carried out at a one-sided 0.05 level of significance using the one-sample z-test of proportions. Only AT and ITT patients who experienced a safety endpoint or had at least 23 days (30 days minus the allowable 7 day visit window) of follow-up will be included in the analyses.

As a secondary analysis, to account for any missing data in the primary endpoint (caused by not experiencing the safety endpoint AND prematurely withdrawing from the study before 23 days of follow-up), a tipping point analysis will be conducted. Here the above safety null hypothesis will be repeatedly tested, first assuming 0 patients with missing data failed (i.e., experienced the safety event), then assuming 1 patient with missing data experienced the safety event, then assuming 2 patients with missing data experienced the safety event, etc. Of interest is the "tipping" point, i.e., the number of Intervention missing data subjects who must be imputed as failures in order for the safety null hypothesis to no longer be rejected.

In addition, in the final analysis, assessments of study-center and of region effect on the primary safety endpoint will be carried out on the interventional group within the AT population using logistic regressions. A 0.15 level of significance will be used to assess the significance of each of the study center and region effects on the safety endpoint. A non-significant result for each of study centers and regions will support the pooling of patients across study centers and across regions for the primary safety analysis. A significant result will require further inspection of the by-center and by-region results to assess if poolability is appropriate. Note that centers with less than 5 subjects will be pooled with other centers by closest geographic region; this pooling will be carried out prior to the unblinding.

In addition, a logistic regression to assess the consistency of the primary safety endpoint rate across the following categories will also be performed on the interventional arm (separately for Phase I and Phase II) within the AT population:

- Subject gender (male versus female)
- Valve prosthesis type (Edwards vs. Medtronic)

- Operative risk (by Society of Thoracic Surgeons [STS] Risk Score)
- Type and duration of antiplatelet therapy:
 - Pre- and peri-procedural therapy:
 - Protocol-recommended antiplatelet therapy vs. other
 - Maintenance therapy:
 - Dual antiplatelet therapy (DAPT) to 90 days vs.
 - Monotherapy (aspirin or clopidogrel) to 90 days vs.
 - Warfarin with antiplatelet therapy to 90 days vs.
 - Other

As above, a 0.15 level of significance will be used to assess the significance of the difference of the primary safety endpoint rate across the subgroups of each factor.

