6.2.3 Withdrawal and Replacement of Patients

Subjects can withdraw from the study at any time; the reason(s) for withdrawal (if given) will be documented. All data available at the time of withdrawal (if any) will be used for analysis. There will be no further follow-up (per this study protocol) on a subject who has withdrawn. Subjects who withdraw from the study will not be replaced. The withdrawal of a subject can be initiated by the Investigator if he/she determines it is in the best interest of the patient.

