12.2 Sample Size Calculation

12.2.1 Hypotheses

12.2.1.1.1 Primary Safety Hypothesis (Phase I and Phase II reported individually)

The primary safety hypothesis is that the rate of the primary safety endpoint (a composite of death, stroke, life-threatening or disabling bleeding, AKI [Stage 2 OR 3], coronary artery obstruction requiring intervention, major vascular complication, and valve-related dysfunction requiring repeat procedure) in the group undergoing TAVI with either protection device system (Intervention Groups) at 30 days will be less in each device group (TriGuard HDH and TriGUARD 3) compared separately to a performance goal (PG) of 34.4%.

Specifically, the primary safety analysis will assess if the Intervention group's safety event rate is significantly less than the PG of 34.4% using a one-sample z-test of proportions. The formal null and alternative hypotheses to be tested are:

$$H_0: \pi \geq 0.344$$

$$H_1: \pi < 0.344$$

where π is the true safety event rate for the Intervention arm.

The primary hypothesis test will be carried out by comparing the upper bound of the one-sided 95% confidence interval of the primary safety endpoint event rate in the intervention arm to the PG. With the planned evaluable sample size of 179 subjects and a one-sided alpha of 0.05, the critical value for rejection of the null hypothesis is 28.5%: if the primary

safety endpoint occurs in 28.5% or less of intervention group subjects, the performance goal will be met.

After accounting for a potential 5% loss to clinical follow-up at 30 days (including subjects who do not meet As Treated population criteria), the total required intervention group sample size is 190 subjects in each Phase. For Phase II 150 subjects randomized to the TriGUARD 3 and the 40-50 roll-ins will constitute the primary safety population.

Trial success depends on both primary endpoints being met in their primary analysis populations; i.e., the primary safety endpoint must be met in the primary (AT) population and the primary efficacy endpoint must be met in the primary (eITT) population in order for the trial to be declared a success. Because both primary endpoints (safety and efficacy) must be met (i.e., both H_0 must be rejected) for the trial to be declared a success, no adjustment to alpha for multiple endpoints is required for the two primary study endpoints.

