12.2.4 Sample Size Estimation

12.2.4.1 Primary Safety Endpoint

The primary safety endpoint is combined safety (VARC-2 defined as a composite of death, stroke, life-threatening or disabling bleeding, acute kidney injury [Stage 2 or 3], coronary artery obstruction requiring intervention, major vascular complication, and valve-related dysfunction requiring repeat procedure), evaluated at 30 days.

Based on published literature of patients undergoing unprotected TAVI (§12.2.2), establishing the expected Control event rate of 25%, and a 37.5% relative margin (absolute delta 9.4%), a Performance Goal (PG) has been set at 34.4% (25% + 9.4%). The primary safety analysis will assess if the Intervention group's safety event rate is significantly less than the PG of 34.4%.

A sample size of 179 evaluable subjects in the intervention group will provide 85% power to determine whether the intervention group meets the PG at the one-sided $\alpha=0.05$ level when using a one-sample z-test of proportions. After accounting for a potential 5% loss to clinical follow-up or dropout from the primary analysis population (As Treated) at 30 days, the total required sample size is 190 subjects in each intervention group. Therefore, the initial randomized sample size of 190 subjects in each intervention group in each phase will have sufficient power to determine whether the intervention meets the safety PG. For Phase II 150 subjects randomized to the TriGUARD 3 and 40- 50 roll-ins will constitute the primary safety population.

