12.4.9 Additional Analyses

The following data will be summarized using descriptive statistics presented by treatment group:

- Subject enrollment and data compliance by site and visit (data compliance at each visit is percent of patients whose data forms have been collected and entered divided by the percent of patients whose forms should have been collected and entered) (ITT, eITT, PT, and AT populations)
- Frequency (number and percent of patients) with each type of concomitant medication (AT population)
- Frequency (number and percent of patients) with each site-reported Treatment Emergent AE overall and by MedDRA system organ class and preferred term (a treatment emergent AE is an AE that started or worsened during or after the index procedure) (AT population)
- Frequency (number and percent of patients) with each site-reported Treatment Emergent Serious AE overall and by MedDRA system organ class and preferred term (AT population)
- Frequency (number and percent of patients) with each site-reported Treatment Emergent AE or SAE, by CEC-adjudicated relationship to the investigational device or procedure (AT population)
- Protocol deviations (number and percentage of patients with each deviation type) (ITT population)
- Kaplan-Meier plots for MACCE and TAVI early safety through 30 days (AT Population; patients without an event will be censored at 30 days or day of withdrawal, whichever is earlier)
- Detailed listings on primary and secondary endpoints, site-reported AE as well as protocol deviations

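### The primary safety analysis drops early withdrawals only if they are event-free, so the tested rate is biased upward and the stated 85% power is not assured

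*Combined protocol and SAP*

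**What the plan says.** Section 12.4.2 tests whether the intervention group's 30-day rate of the combined safety endpoint is "significantly less than 34.4% using a one-sample z-test of proportions". On who is counted, it says: "Only AT and ITT patients who experienced a safety endpoint or had at least 23 days" of follow-up, which is day 30 less the 7-day visit window. The remaining subjects are called missing, and missingness is described as "caused by not experiencing the safety endpoint AND prematurely withdrawing from the study before 23 days of follow-up". A secondary tipping-point analysis adds these subjects back, first with none of them as failures, then one, then two, and so on.

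On size, section 12.2.4.1 says: "A sample size of 179 evaluable subjects in the intervention group will provide 85% power". Section 12.2.1.1.1 gives the cut-off: "With the planned evaluable sample size of 179 subjects and a one-sided alpha of 0.05", the null is rejected at an observed rate of 28.5% or less. The 179 is raised to 190 for a 5% loss, and that 5% also covers subjects who do not meet the As Treated criteria. In Phase II the safety set is 150 randomized subjects plus 40 to 50 roll-ins, that is 190 to 200.

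Two other sections treat withdrawals differently. Section 6.2.3: "All data available at the time of withdrawal (if any) will be used for analysis". Section 12.4.9 plans Kaplan-Meier plots of early safety to day 30 in the As Treated population, where "patients without an event will be censored at 30 days or day of withdrawal, whichever is earlier". Section 5.4.1.1 shows that this is the same composite as the primary safety endpoint.

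**The concern.** Among subjects who leave before day 23, inclusion depends on the outcome. One with an event counts in the numerator and the denominator; one without an event counts in neither. Every deleted subject is event-free as far as is known, so the expected rate can only stay the same or rise.

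The sample size treats the 179 evaluable subjects as if they carried the full design rate of 25% unchanged, which means that losses are taken as unrelated to outcome. Under this rule they are not.

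Section 12.2.1.1.1 makes trial success depend on both primary endpoints, and the hypothesis-driven secondary endpoints are tested only if the primary hypotheses are confirmed. A device that performs exactly as assumed could therefore miss the safety goal more often than the protocol states, and its reported event rate would be too high.

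**Working it through.** **Inputs from the documents.** Goal p0 = 0.344; expected rate 0.25; one-sided alpha 0.05; 179 evaluable; 5% loss; 190 enrolled (up to 200 in Phase II).

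**Assumed, because the documents do not say.** How much of the 5% is early withdrawal, and what share f of the withdrawers' events occur before they withdraw. The documents give only that more than half of strokes fall in an early phase within 2 days (section 4.1.2.1) and that kidney injury is assessed to 7 days (Appendix I).

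**1. The plan's own figure.** Power = Φ[(p0 − p − 1.645·√(p0(1−p0)/n)) / √(p(1−p)/n)].

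With n = 179 and p = 0.25: (0.094 − 0.0584)/0.0324 = 1.10, so power is 86.4% against the stated 85%. The cut-off is 0.344 − 0.0584 = 28.6%, and 51/179 = 28.5%. For the inflation, 179/0.95 = 188.4, against 190 stated. The plan's figures reproduce.

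**2. The rule applied.** Let d be the share withdrawing before day 23, unrelated to eventual outcome.

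- Share included = 1 − d(1 − 0.25f)
- Expected rate = 0.25[(1 − d) + d·f] / share included

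For N = 190 and d = 0.05, using the power formula above:

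| Withdrawers' events that precede withdrawal | Expected rate | n analysed | Power |
|---|---|---|---|
| None (f = 0) | 25.0% | 180.5 | 86.7% |
| 25% | 25.2% | 181.1 | 85.0% |
| 50% | 25.5% | 181.7 | 83.2% |
| 75% | 25.7% | 182.3 | 81.3% |
| All (f = 1) | 0.25/0.9625 = 26.0% | 182.9 | 79.3% |
| Every deleted subject event-free, no event lost | 0.25/0.95 = 26.3% | 180.5 | 75.6% |

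In the last row withdrawal is related to outcome; in the others it is not.

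**3. Other sizes and splits.**

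- N = 200, d = 0.05: 85.0% at f = 0.5, 81.2% at f = 1, 77.5% if all deletions are event-free.
- Half of the 5% are non-As-Treated exclusions, f from 1 to 0.5: about 84 to 86% if 190 As Treated subjects remain with 2.5% early withdrawal. It is about 83 to 85% if the excluded 2.5% also come off the 190 (n start = 190 × 0.975 = 185.25, d = 0.025/0.975).
- Randomization extended to 295 (assumed about 197 device subjects plus 40 roll-ins = 237), d = 0.05, f = 1: 86.9%.

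**4. Simulation against Kaplan-Meier.** N = 190, true rate 25%, 5% withdrawing uniformly over days 2 to 23 independently of events, 50 to 95% of events in days 0 to 2 (all assumptions). The plan's rule gives a mean rate of about 25.7 to 25.9% and power of about 81 to 83%. The Kaplan-Meier 30-day rate, with Greenwood variance on the log-log scale, averages 25.0% with power of about 87 to 89%.

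**5. Direction of the error.** At a true rate of 34.4%, N = 190 and d = 0.05, the rule's expected rate is 0.344/(1 − 0.05 × 0.656) = 35.6% at f = 1, or 0.344/0.95 = 36.2% if all deletions are event-free. The type I error is then about 2.4% and 1.6% by simulation, against a nominal 5%.

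**The case against.** The strongest reply is that the rule works against the device. It lowers the type I error, so a positive safety finding is more secure, and the cost falls on the sponsor as a few points of power. That stands.

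A reader might go further than the documents allow in two ways.

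- **That power is simply not delivered at the plan's own 5% loss, and is 75 to 80%.** The documents do not support this. The 5% includes subjects outside the As Treated population, whose exclusion does not depend on outcome. Event timing is not given for bleeding, vascular, valve or fatal events. If only a quarter of the withdrawers' events come first, power is 85.0%. Values near 74% need about 7.5% early withdrawal, which is above the plan's allowance.
- **That 12.4.2 flatly contradicts 6.2.3 and 12.4.9.** Section 6.2.3 is a general statement on conduct and 12.4.2 a specific rule. Section 12.4.9 plans descriptive plots, not a rival test. The deleted subjects do return in the tipping-point analysis, whose first step counts them all as event-free. The sections are in tension and should be aligned.

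The tipping-point analysis does not settle the matter. It is secondary, it looks for the point at which a rejection is lost, and it leaves the primary estimate as it is. Its first step also errs the other way, by counting as event-free anyone lost before a later event.

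It is also fair that Kaplan-Meier is unbiased here only because withdrawal was taken as non-informative. That is an assumption too, and a reason to keep the tipping-point analysis.

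**Conclusion.** The point holds as a conditional one. The rule's asymmetry and its upward direction follow from the wording alone. The size is 0 to 1.3 percentage points at 5% early withdrawal, and the sample size does not allow for it.

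At a true rate of 25% and N = 190, if the whole 5% is early withdrawal, power is about 79 to 83% when half or more of the withdrawers' events come first. It is about 76% if every loss is event-free, and about 87% if no event precedes withdrawal. At N = 200 the corresponding range for half or more is about 81 to 85%. If half of the 5% are non-As-Treated exclusions, power stays within about 2 points of 85%. All but the 76% figure take withdrawal as unrelated to outcome.

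A positive safety conclusion is not put in doubt. The consequences are an overstated event rate and a stated power that is not assured. Because the better analysis is already half planned, the change is worth making.

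**What to change.** Make the primary safety estimate the Kaplan-Meier 30-day event rate in all As Treated intervention subjects, with the Phase II roll-ins included as now, censored at withdrawal. Compare its one-sided 95% upper bound (Greenwood variance, log-log scale) with 34.4%. Death is part of the composite, so it is not a competing risk. State the censoring day for event-free subjects whose visit falls on days 23 to 29.

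Keep the 23-day rule with the z-test, and the tipping-point analysis, as sensitivity analyses; the latter covers informative withdrawal. Align the wording of 12.4.2 with 6.2.3 and 12.4.9.

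If the present rule stays primary, replace the flat 85% with a range under stated withdrawal and timing assumptions, about 76 to 87% at N = 190.

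The cost is wording in the protocol and SAP, since a Kaplan-Meier display of this endpoint is already planned. The drawback is that the test is no longer a simple binomial z-test and the 28.5% cut-off becomes approximate.
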